- 39. Nielsen J. The usability engineering life cycle. Computer. 1992;25(3):12-22.

PART II: STATISTICAL ANALYSIS PLAN

Statistical Analysis Plan

Data will be analyzed using R version 4.2.1.

Primary Outcome: Chabot Component Effects on Self-Reported Receipt of Treatment and/or Services Utilization

Analyses will be executed using discrete time survival analysis and will reflect the proportional increase in odds of treatment and/or services utilization corresponding to receiving each chatbot component (motivational interviewing, psychoeducation, personalized recommendations, repeated administration). This approach estimates the effect of independent variables (i.e., chatbot components) on the occurrence of an event (i.e., treatment utilization). Models will be fit with treatment use regressed on follow-up time (2-week, 6-week, or 14-week) and each chatbot component. Models will not incorporate an intercept; this allows for estimation of treatment utilization odds among participants who have yet to report seeking treatment. The model will be estimated using a logit link, and for all coefficients, odds ratios and 95% confidence intervals will be computed. Parameters of primary interest include the time effects, which reflect odds of treatment seeking at each time point, as well as the main effects of each chatbot component. Censoring and missing data were accommodated using maximum likelihood estimation.

Primary Outcome: Time Effect on Help-Seeking Attitudes (Motivation and Willingness to Change and Seek Help)

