Clinical or subclinical EDs impact 10% of individuals in their lifetime, which translates to at least 30 million people in the U.S.¹ Although evidence-based treatments for EDs have been established,² <20% of individuals with EDs receive treatment,³;⁴ which is problematic given that lack of or delays in treatment result in poorer prognosis and greater relapse.⁵ While few individuals with an ED receive treatment specifically for their disorder, these individuals exhibit elevated health services use and costs compared to those without an ED.⁶ The problem of access to care for EDs is even worse amongst racial/ethnic minority individuals.⁻¹¹ Receiving services for a psychiatric disorder involves multiple steps, with identifying or learning one's symptoms are something in need of help being a crucial first step.⁴ Yet even once symptoms are identified, individuals with EDs may experience numerous barriers to care, including stigma, denial of illness severity, lack of knowledge about resources, and practical barriers such as cost.¹¹⁰ We need a novel solution to not only identify individuals with EDs but to also encourage mental health services use and address treatment barriers.

C2. Prior Literature and Studies

A conversational agent or "chatbot" has great potential for increasing mental health services use among those with EDs. People respond psychologically to chatbots as if they are people, even when they are aware they are conversing with a robot. ^{11;12} In one study, when people talked to an automated chatbot, they were less fearful of self-disclosure and displayed more intense sadness compared to those who thought the chatbot was human-controlled. ¹³ There is optimism regarding a role for chatbots in mental health; ^{11;14} the scalability, cost-effectiveness, and anonymity they provide make them ideal for delivering mental health interventions.

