We will document recruitment rates (i.e., percent of those offered participation in the study who sign up), as well as study retention rates, to assess appropriateness of follow-up procedures. Demand for the chatbot will be measured as: 1) number of texts to the chatbot; and 2) engagement at repeated administrations (if randomly assigned to this condition).

To validate receipt of treatment, a study team member will contact a random subset of participants (i.e., approximately 10%) who reported engaging in some kind of treatment to solicit additional details on their service use and experience through phone/Zoom call or online questionnaire, which will provide additional validation, and when possible, participants will also be asked to provide some kind of documentation for the services they reported using (e.g., send receipt of therapy session or provide email indicating they signed up for a recommended online program).

Participants will receive invitation and reminders via email, phone, and/or text message for each assessment, and if they have not completed the conversation with the chatbot. Participants may receive thank you messages for completing assessments.

PHI discussions via email will use WashU guidelines: 1) a test email will be sent to the participant to verify their identify (confirm correct recipient) and that this email will be sent in a secure manner (i.e., [secure] in subject line); 2) The body of the email will instruct the participant to send all information as a response to this thread and to not remove the "[secure]" from the subject line; 3) document in our research records the participant's agreement to provide information over email.

E2. Subject Selection and Withdrawal

E2.A. Inclusion Criteria

U.S. resident; English-speaking; age 18 years or older; own a smartphone; screen positive for a DSM-5 clinical or subclinical eating disorder; not receiving treatment for an eating disorder

E2.B. Exclusion Criteria

We will exclude participants who are currently receiving treatment for an eating disorder given the goal to increase access to services for those not receiving help. In addition, we do not plan on enrolling individuals who screen for Avoidant Restrictive Food Intake Disorder.

E2.C. Ethical Considerations

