It is important to note that in previous similar clinical trials of digital health interventions, the procedures outlined above have been used to protect against and minimize potential risks to

participants, and they have proved effective in preventing emotional and physical complaints as well as adverse events.

E2.D. Participant Recruitment Plans and Consent Process

We plan to enroll approximately 200 English-speaking adults ≥18 years with a DSM-5 clinical or subclinical eating disorder who own a smartphone and are not in treatment for an eating disorder.

Participants will be recruited from the NEDA online screen. Once an individual screens positive for a clinical/subclinical ED, is not currently in treatment, and is ≥18 years old, they will be given a link to the Qualtrics eligibility screen. If an individual endorses owning a smartphone and being a U.S. resident, they will be shown the consent form in Qualtrics and will be asked to either agree to or decline participation in the study. Individuals will be encouraged to call a member of our research team to discuss the study.

E2.E. Randomization Method

Study 2 will use a 2⁴ full factorial trial design to test the four binary chatbot components: psychoeducation, motivational interviewing, personalized recommendations, and repeated administration. Thus, there are 16 experimental conditions, and participants will be randomized to 1 of those 16 conditions. Participants can be assigned to intervention ("yes") or control ("no") conditions for each chatbot component.

Risks

There are minimal risks for participants.

Physical Risks: N/A

Psychological Risks: Our proposed chatbot designed to facilitate mental health problems may promote increased focus on mental health symptoms in some individuals. It is also possible that participants may feel uncomfortable disclosing information about certain behaviors such as disordered eating. However, we have asked questions of a similar nature in several studies in the past and have not had participants report discomfort.

Social Risks: There may be some embarrassment related to completing questions related to disordered eating symptoms.

Financial Risks: N/A

Legal Risks: N/A

Risks to Privacy: We will go to great lengths to keep participant information private and confidential. Participant confidentiality will be maintained in compliance with HIPAA regulations.

Other Risks: N/A

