Taking part in this research study is voluntary. Participants may choose not to take part in this research study or may withdraw their consent at any time. They may withdraw by telling the research team they are no longer interested in participating in the study or they may send in a withdrawal letter. There will be no penalty or loss of benefits to which they were otherwise entitled.

E2.I. Data Collection and Follow-up for Withdrawn Subjects

When a participant withdraws from the study, the research team will stop collecting data from them.

F. Study Procedures

F1. Screening for Eligibility

Eligibility will be assessed using the NEDA eating disorder screen and eligibility questions in Qualtrics.

F2. Schedule of Measurements

Measure	NEDA Screen	Baseline Assessment	Chatbot Use	2 Week	6 Week	14 Week	Explanation/ Primary Purpose
SWED	X						To determine if the individual has a clinical/subclinical ED and to determine if they are in treatment.
Demographic Questions	x	Х					To determine if individuals are 18 years or older. To obtain demographic information for analyses.
Recruitment Rates	Х	Х					To obtain the percentage of those offered participation who enroll.
Retention Rates				X	Х	x	To obtain the percentage of follow-up completion.
Demand for Chatbot			X				Number of texts sent to the chatbot and engagement with repeated administration, if applicable.
SUS and USE				Х	Х		To examine usability of the chatbot.

Target measure: motivation for treatment and mental health services use questions	х	Х	х	х	To determine motivation for treatment and mental health services use.
Target measure: SE- KNOW	Х	Х	x	x	To determine self- efficacy in help seeking.
Target measure: personal relevance question	Х	Х	Х	х	To determine efficacy of personalized recommendation component.
Target measure: Dissonance Thermometer	Х	X	x		To determine efficacy of motivational interviewing component.
Target measure: opportunity question	X	х	Х	Х	To determine efficacy of repeated administration component.
Target measure: EDs Literacy Scale	Х	X	×	Х	To determine efficacy of psychoeducation component.
EDE-Q	Х		Х	Х	To examine ED symptoms.
EDs Quality of Life Scale	Х		Х	Х	To examine quality of life.
Patient Health Questionnaire 9	Х		х	Х	To examine depression.
Generalized Anxiety Disorder 7	Х		Х	Х	To examine anxiety.
Treatment and Barriers to Care Questions	Х		X (if no to receiving treatme nt)	X (if no to receivin g treatme	To determine any barriers to treatment utilization.

l					
ı				nt)	

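### The primary event is not limited to care begun after baseline, so participants already in other mental health care can be scored as week-2 events, which dilutes any real component effect

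*Combined protocol and SAP*

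**What the plan says.** **Entry.** Protocol E2.A requires participants who "screen positive for a DSM-5 clinical or subclinical eating disorder; not receiving treatment for an eating disorder". E2.B repeats the limit: "We will exclude participants who are currently receiving treatment for an eating disorder". Neither mentions other counselling, medication or services. Some wording elsewhere lacks the eating-disorder qualifier: E2.D describes someone who "is not currently in treatment, and is ≥18 years old", and the F2 schedule uses the SWED screen "to determine if they are in treatment".

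**Event.** The SAP's first primary outcome is "Component Effects on Self-Reported Receipt of Treatment and/or Services Utilization". The text below that title glosses the event only as use of treatment. Protocol D2 and F4 call the outcome mental health services use. By contrast, the willingness item in the SAP's second primary outcome names psychotherapy for eating, shape or weight concerns.

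**Model.** A no-intercept discrete-time logit model with three follow-up times (2, 6 and 14 weeks) and the four components, plus interactions. It has no baseline service-use term. The time effects and component main effects are the parameters of primary interest.

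**Baseline data.** The F2 schedule lists a set of questions with the purpose "To determine motivation for treatment and mental health services use". The table is broken in extraction, but the row carries four marks, which read as baseline, 2, 6 and 14 weeks. The SAP gives no rule for using the baseline answers.

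**The concern.** The entry criterion and the event do not match. Consider an eligible participant who is already seeing a counsellor for depression. At week 2 she truthfully reports using a mental health service. Under the event as written she can be scored as a first event and leave the risk set, although nothing changed after randomisation.

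Such participants are foreseeable. The study abstract cites comorbid psychopathology, and F2 schedules depression and anxiety measures. C1 contrasts the few who are treated for the eating disorder itself with the group's overall use: "these individuals exhibit elevated health services use and costs compared to those without an ED".

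The week-2 odds would then mix care already under way with new help-seeking, and a component that does prompt new help-seeking would look weaker than it is. F4 says that component effect sizes will decide what is retained in the optimised chatbot and will power the next trial. The SAP also uses p ≤ .05 to define a sufficiently large main effect, which controls whether interactions are probed. Finally, the attitudes analysis keeps only participants who report no treatment seeking at follow-up, so the same people can drop out of that analysis too.

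**Working it through.** The plan gives no power, target odds ratio, event rate or dropout, so it has no figure of its own to reproduce. The calculation below shows direction and plausible size only.

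**Inputs from the documents.** About 200 participants (E2.D); assessments at 2, 6 and 14 weeks, so intervals of 2, 4 and 8 weeks; the SAP's no-intercept logit model.

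**Assumptions.** Equal allocation, so 200/2 = 100 per level of one component; other components ignored; true odds ratio 2.0 for new use; 2% new use per week in the component-off level; no dropout; a share π already in other care, all reporting use at week 2.

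**Step 1, new-use hazards.** Component off, h = 1 − 0.98^w: 0.0396 (w = 2), 0.0776 (w = 4), 0.1492 (w = 8). Component on, with the odds doubled: 0.0762, 0.1440, 0.2596.

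**Step 2, expected counts at π = 20%.** Week-2 events:
- off: 20 + 80 × 0.0396 = 23.17 of 100, odds 23.17/76.83 = 0.302
- on: 20 + 80 × 0.0762 = 26.09 of 100, odds 26.09/73.91 = 0.353

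The week-2 odds ratio is 0.353/0.302 = 1.17 instead of 2.00. Prevalent users have then left the risk set, so the later intervals keep an odds ratio of 2.00. The dilution arises in the first interval, and the common odds ratio averages over all three.

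**Step 3, fit the model to the expected counts.** At π = 20% the log odds ratio is 0.419 with SE 0.235, so the odds ratio is e^0.419 = 1.52 and z = 0.419/0.235 = 1.78. The last column shows the same trial with baseline users removed. The odds ratio is then 2.00 throughout and z = 2.52 × √(1 − π).

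| π | Fitted OR | Expected z | Fitted week-2 odds, component off | z if baseline users are removed |
|---|---|---|---|---|
| 0% | 2.00 | 2.52 | 0.04 | 2.52 |
| 5% | 1.81 | 2.29 | 0.08 | 2.46 |
| 10% | 1.69 | 2.10 | 0.13 | 2.39 |
| 20% | 1.52 | 1.78 | 0.26 | 2.25 |
| 30% | 1.42 | 1.53 | 0.43 | 2.11 |
| 40% | 1.35 | 1.31 | 0.66 | 1.95 |

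The fitted week-2 odds at 20% (0.26) are below the raw 0.302 because the model forces one odds ratio across intervals.

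**Step 4, other assumptions.** With a control hazard of 10% in every interval, the fitted odds ratio is 1.85, 1.74, 1.59, 1.49 and 1.42 at 5, 10, 20, 30 and 40%. At 20%, power is 0.50 as written and 0.66 after removal. Still at 20%, a 5% hazard gives 1.42 and hazards of 20, 15 and 15% give 1.72.

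**Step 5, null component.** With a true odds ratio of 1.0, both levels have the same expected counts in every interval, so the fitted odds ratio is 1.00 at any π.

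**The case against.** The strongest reply is that the plan is silent rather than wrong. The questionnaire items are not in the documents. If the follow-up item asks about newly started care, or only about eating-disorder care, this dilution disappears. Some eligibility wording says simply not in treatment. The SAP also speaks of treatment seeking, and one E1 example of documentation is signing up for a recommended online program; both suggest new care. The risk set, people who have not yet reported seeking treatment, could be read as already removing baseline reporters.

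Part of this stands. A reader might infer that people in other care will certainly be counted as events. The documents do not establish that; they only fail to prevent it. A reader might also infer that every component odds ratio is biased, or that the next trial's inputs are wrong. Null components are unaffected, no false positives arise in expectation, and the share in other care is not given. C1 concerns health services in general, so it supports no figure for concurrent mental health care. Nor do the documents show that an outcome covering all mental health services is an error: it is the outcome that the protocol declares.

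What does not stand is that existing text closes the gap. The formal criteria in E2.A and E2.B are eating-disorder-specific. The SAP never says that a baseline report removes anyone; where it spells out the reports that matter, for the attitudes subset, it names only the three follow-ups. The barriers items in F2 are routed by whether the person is receiving treatment, which is a status and not a start. The validation call covers about 10% of reporters and specifies no check of start date.

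**Conclusion.** The concern holds in conditional form. Entry excludes only current eating-disorder treatment, the event as written is not restricted to new care, and the model ignores baseline service use. Continuing care can therefore be scored as a week-2 event regardless of assignment, inflating the week-2 time effect and shrinking non-null component effects.

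The size rests on unverified assumptions, chiefly the prevalent share and the requirement that every baseline user reports use at week 2, which is the worst case. Under the main set, a true odds ratio of 2.0 appears as 1.81 at a 5% share and 1.35 at 40%, and expected z drops below 1.96 somewhere between 10% and 20%. That crossing point moves with the assumed rate of new use. With no prevalent users, or with items already limited to new care, there is no dilution from this source.

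**What to change.** In the SAP:

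1. Define the primary event as a treatment or service first begun after completion of the baseline assessment.
2. Use the baseline services-use items so that continued use of a service already reported at baseline is not an event. Alternatively, remove baseline users from the risk set, in the main analysis or as a sensitivity analysis. Either rule rests on answers given before randomisation, so the randomised comparison is preserved.
3. Apply the same rule when forming the subset for the attitudes analysis.
4. State whether the event covers eating-disorder services only or any mental health service. That is the sponsor's choice, since narrowing it changes the declared outcome.
5. Quote the baseline and follow-up item wording. If the items already ask about newly started care, one sentence settles the matter.

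The cost is a few lines of SAP text, provided that the baseline items record current services. The downside is fewer nominal events and, if baseline users are removed, a smaller sample: the last column of the table shows z falling from 2.52 to 2.25 at a 20% share, against 1.78 if they are counted.

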We have used a user-centered design approach to create a single chatbot prototype, which includes four key features: 1) providing a personalized recommendation for seeking intervention; 2) engaging the user in motivational interviewing to overcome barriers to care; 3) education on the seriousness and health consequences of eating disorders; and 4) repeated check-ins with the user to encourage follow-up with care.

Study 2 will use a 2⁴ full factorial trial design to test the four binary chatbot components. Thus, there are 16 experimental conditions, and participants will be randomized to 1 of those 16

conditions. Participants can be assigned to intervention ("yes") or control ("no") conditions for each chatbot component.

Participants will be recruited from those who complete the NEDA online screen and who meet eligibility criteria of screening positive for a clinical/subclinical ED, at least 18 years old, and not currently in treatment for an ED. For a period of time on the NEDA site, eligible users will be offered the chatbot. Interested individuals will be taken to a Qualtrics screen wherein those who endorse owning a smartphone and being a U.S. resident will be given access to participate in our study. Data from the NEDA eligibility screen will be collected. The consent form will be shown via Qualtrics and will encourage interested individuals to call a member of our research team to discuss the study. Once a participant completes the baseline measures, they will be randomized using Qualtrics. Once the baseline measures are completed, participants will be given information on how to access the chatbot and their unique chatbot start code.

Participants will engage with the chatbot for between 5-20 minutes, dependent on condition. Participants who are randomized to the repeated administration module will complete approximately 3 new conversations over the course of 2 weeks. The chatbot will automatically reach out to a participant if they do not complete a conversation within 1 day.

Assessments will occur online and may include data from the initial ED screen completed on the NEDA website. Assessments will take place at baseline (i.e., prior to chatbot use), and at approximately 2, 6, and 14 weeks after baseline completion via Qualtrics (see *F.2 Schedule of Measurements*).

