Of note, all models will include estimates of interaction effects in addition to main effects of each chatbot component. To guide the interpretation of interaction effects, we will follow the guidelines of Collins et al. (2014). These guidelines suggest that significant interaction effects in factorial experiments have a bearing on decision-making regarding the best overall treatment package if at least one of the components involved in the interaction has a sufficiently large main effect. We define sufficiently large main effects as those with p values \leq .05 or with 95% confidence intervals that do not include 0. Thus, interaction effects will be probed and interpreted if at least one component involved in the interaction has a significant effect alone.

References

1. Collins, L. M., Trail, J. B., Kugler, K. C., Baker, T. B., Piper, M. E., & Mermelstein, R. J. (2014). Evaluating individual intervention components: Making decisions based on the results of a factorial screening experiment. *Translational Behavioral Medicine*, 4, 238–251.

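### The services-use model names no baseline covariate; prespecifying the clinical/subclinical screen category would be a cheap improvement of modest and conditional benefit, not the repair of an error

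*Combined protocol and SAP*

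**What the plan says.** The SAP (first Primary Outcome, receipt of treatment and/or services utilization) specifies a discrete-time survival model without an intercept: "Models will be fit with treatment use regressed on follow-up time (2-week, 6-week, or 14-week) and each chatbot component". The effect measure is the odds ratio: "The model will be estimated using a logit link, and for all coefficients, odds ratios and 95% confidence intervals will be computed". The SAP's closing paragraph widens the model, since "all models will include estimates of interaction effects in addition to main effects of each chatbot component". No baseline variable is named in this or any other SAP model.

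The protocol places the screen category before randomisation:

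- E2.A admits people who "screen positive for a DSM-5 clinical or subclinical eating disorder", so both severity classes enter.
- F2 schedules the SWED at the NEDA screen, with the purpose "To determine if the individual has a clinical/subclinical ED and to determine if they are in treatment".
- E1 says of the screen: "Data from the NEDA eligibility screen will be collected".

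E2.E says that "participants will be randomized to 1 of those 16 conditions". It mentions neither blocking nor stratification, whether to adopt or to exclude them. E2.D gives the size: "We plan to enroll approximately 200 English-speaking adults". No power, effect size, event rate or dropout figure stands behind that number.

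**The concern.** Clinical and subclinical participants may differ in how readily they enter treatment. The documents do not say so, but C1 makes it plausible: it lists denial of illness severity among the barriers to care and calls recognising that one's symptoms need help a crucial first step.

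If screen status does predict services use, a logit model that omits it estimates component odds ratios closer to 1 than those within a severity class, and gives up some power. That would matter in two places. Under F4, component effect sizes inform which components to keep and are used to power the next trial. Under the SAP's closing paragraph, p ≤ .05 (or an interval excluding 0) defines a sufficiently large main effect, which in turn decides whether interactions are interpreted. A small loss in the test statistic near that threshold could change a decision.

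**Working it through.** The plan offers no power figure to reproduce, so the check is of size under stated assumptions.

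**Inputs from the documents.** About 200 participants (E2.D); four two-level components (E2.E); follow-up at 2, 6 and 14 weeks (E1); logit link and a .05 threshold (SAP).

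**Assumed inputs.** Equal allocation, so about 100 'yes' and 100 'no' per component; 60% clinical; hazard about 12% per interval; component odds ratio 2; odds ratio for clinical v subclinical (screen OR) from 1 to 4; main effects only.

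**Step 1: chance imbalance.** The 95% limit for the difference in share clinical between the two levels of a component is 1.96 × √(2 × 0.6 × 0.4 / 100) = 0.136, or about 14 points. An imbalance of that size multiplies a component odds ratio by roughly exp(0.136 × ln(screen OR)):

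- screen OR 2: exp(0.136 × 0.693) = 1.10
- screen OR 3: exp(0.136 × 1.099) = 1.16

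The standard error of the component log odds ratio is about 0.25 to 0.32, so the 95% interval already reaches a factor of exp(1.96 × 0.25) = 1.63 to exp(1.96 × 0.32) = 1.87 each way.

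**Step 2: validity without the covariate.** In simulations with no component effect (3,000 runs per scenario, 50% or 80% clinical, screen OR 1 to 3), the unadjusted log odds ratio averaged about 0. Its model standard error (0.251 to 0.315) matched its empirical standard deviation (0.249 to 0.323). Type I error was about 4 to 6% with or without the term.

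**Step 3: power.** Change in power from adding the term, under the assumed inputs above, in three separate sets of simulations:

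| Screen OR | Main set | Repeat 1 | Repeat 2 |
|---|---|---|---|
| 1 | 0 | −0.2 | not run |
| 1.5 | 0 | +0.4 | not run |
| 2 | +0.7 | +1.6 | +2 (78 to 80%) |
| 3 | +3.5 | +2.6 | +3 (78 to 81%) |
| 4 | +5.2 | +3.9 | +7 (74 to 81%) |

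The two repeats used 1,500 runs per scenario. A single power estimate near 78% then has a simulation standard error of √(0.78 × 0.22 / 1500) = 1.1 points, so differences of a point or two between columns should not be over-read.

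Other inputs (component OR 1.8, 50% clinical) give gains of the same order:

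- screen OR 2, about 48 events: 46.7 to 47.9%
- screen OR 2, about 76 events: 63.3 to 65.4%
- screen OR 3, about 78 events: 58.6 to 63.9%

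**Step 4: where the gain comes from.** In the last of these scenarios the log odds ratio averages 0.553 (standard error 0.254) unadjusted and 0.596 (0.260) adjusted. The ratios are 0.553/0.254 = 2.18 and 0.596/0.260 = 2.29. The standard error rises, and the gain comes from the larger estimate. As odds ratios the means are 1.739 and 1.815. With a component odds ratio of 2 and 60% clinical, the mean odds ratio is about 2.05 adjusted and 1.93 to 1.96 unadjusted at screen OR 3 to 4.

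**Step 5: accuracy.** Root mean squared error of the log odds ratio around the true conditional value (60% clinical, component OR 2), unadjusted v adjusted: 0.284 v 0.290 (screen OR 2), 0.279 v 0.287 (OR 3), 0.265 v 0.275 (OR 4). Adjustment does not reduce it.

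**The case against.** The strongest case for leaving the model alone has five parts.

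- **The prognostic link is undocumented.** C1 lists barriers for people with eating disorders in general and does not compare clinical with subclinical cases. The split is not given either. With a screen OR of 1 to 1.5 there is nothing worth gaining. This stands, and makes the benefit conditional.
- **The unadjusted odds ratio is a valid marginal effect.** The pull toward 1 is non-collapsibility, a difference between two estimands. This stands. Adjustment is a choice, and the SAP would have to state it.
- **For a trial meant to generate effect sizes, adjustment brings no better accuracy.** Step 5 bears this out.
- **A two-level term is coarse.** F2 also collects the EDE-Q and motivation at baseline. The screen category has the advantage of being an entry criterion, so it should exist for everyone enrolled, but it removes only the between-class part of any prognostic spread.
- **The interactions are a heavier burden than one omitted term.** With all interactions fitted and about 66 events, 16 to 25% of simulated fits failed to converge or were unstable, with or without the covariate. That is a separate matter and does not argue against the term.

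A reader might go further and infer that chance imbalance in severity biases every component effect. The plan does not support that: over repeated randomisation the imbalance averages to zero, and the standard error already allows for it (Steps 1 and 2). A reader might also infer that allocation is unstratified; E2.E is silent, and silence does not settle it. Nor do the retain-or-drop decisions rest on these odds ratios alone, since D2 names motivation as a second main outcome.

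**Conclusion.** This is a low-cost improvement, not an error in the plan. The omission is plain from the text: follow-up time, components and interactions, with no baseline covariate, although the screen category is known before randomisation. The planned tests and intervals remain valid. The benefit of adding the term runs from nothing, if screen status does not predict services use, to about 3 to 5 points of power and removal of a modest pull toward 1 at a screen OR of 3 to 4. For a screen OR up to 2 the gain is under 1 point in the main simulations and no more than about 2 in the repeats. These sizes rest on the assumed 60% clinical share, event rate, component odds ratio and screen OR, and on a main-effects model without dropout.

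**What to change.** In the SAP's services-use section, add one sentence that prespecifies the SWED screen category (clinical v subclinical) as a fixed covariate in the discrete-time model, and state that the component odds ratios are conditional on it.

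The data come from the eligibility screen, so no new collection is needed, only the transfer of the category into the analysis file. The cost is one more parameter, a slightly larger standard error on the log odds ratio (for example 0.254 to 0.260 in Step 4), and a conditional odds ratio in place of an unadjusted one. Simulated type I error stayed at about 4 to 6%. Fixing the choice in advance also removes discretion over later adjustment.
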